5.1.14.2 Compliance with accelerated elimination procedure

Subjects' compliance with the elimination procedure will be reviewed and assessed after each elimination procedure. The recommended compliance should include intake of 33 doses of cholestyramine (8 g or 4 g) or 22 doses of activated charcoal (50 g). Plasma concentration of teriflunomide should not serve to assess compliance. Please refer to Sections 5.1.5.2 and 5.1.14.4 for timing of teriflunomide testing after EOT.

Note: At FU1 and (abbreviated) FU2, plasma concentration of teriflunomide will not be measured. The testing should occur as described in Section 5.1.14.4.

For subjects not entering the AC-058B303 extension study, subjects compliance will be reviewed at FU1. If the compliance has been assessed by the investigator as not sufficient at FU1, the subject will be asked to complete missing intakes or repeat the procedure. In such a case a new compliance assessment will be performed at FU2. If the compliance has been assessed as not sufficient at FU2, washout may be obtained through additional elimination procedures or by waiting for several months of natural elimination according to the subject's preferences. Duration of continued contraception and timing of teriflunomide testing are described in Section 5.1.14.4.

For subjects entering the AC-058B303 extension study, compliance will be reviewed at FU1. If the compliance has been assessed as not sufficient at FU1, the investigator will

Ponesimod / ACT-128800 Relapsing multiple sclerosis Protocol AC-058B301, OPTIMUM Version 7 5 December 2018, page 113/376

Confidential

decide if the elimination procedure should be repeated or missing intakes completed. In such a case a new compliance assessment will be performed at an abbreviated FU2. The abbreviated FU2 should be scheduled to allow enough time for completing the elimination procedure. The subject will only be eligible to enter the extension study AC-058B303 if the compliance was assessed as sufficient at FU1 or abbreviated FU2. Duration of continued contraception and timing of teriflunomide testing are described in the AC-058B303 extension study protocol. If the compliance has been assessed as not sufficient at abbreviated FU2, the subject will not be eligible to enter the extension study AC-058B303. In such a case, teriflunomide washout may be obtained through additional elimination procedures or by waiting for several months of natural elimination according to the subject's preferences. Duration of continued contraception and timing of teriflunomide testing are described in Section 5.1.14.4.

5.1.14.3 Accountability of accelerated elimination procedure treatment

At FU1 and FU2 (if accelerated elimination procedure was repeated after FU1), the number of bottles (activated charcoal) or sachets (cholestyramine) dispensed and returned, and the dosages administered are recorded on the non-IMP accountability log by the site staff. The accelerated elimination procedure treatment accountability is checked by the monitor at EOS. If the accountability cannot be performed (e.g., subject doesn't return bottles or sachets), compliance will be evaluated based on discussions with the subject.

5.1.14.4 Duration of continued contraception after EOT

Contraception measures as described in Section 4.5, must be continued until at least 6 weeks after the first of two consecutive tests showing a teriflunomide concentration < 0.02 mg/L. The testing of teriflunomide plasma concentration may be conducted for WOCBP and fertile male subjects, if needed, to confirm that contraception can be discontinued.

For subjects not participating in the AC-058B303 extension study, plasma concentration of teriflunomide must not be measured earlier than 20 weeks after the last study drug intake, and provided the subject has been compliant with the accelerated elimination procedure of teriflunomide [see Section 5.1.14.2]. If the subject has not been compliant with the accelerated elimination procedure, testing for teriflunomide must not be done before 35 weeks (i.e., 8 months) after last dose of study drug or EOS, whichever comes last.

- If teriflunomide plasma concentration is as anticipated less than 0.02 mg/L, the site will receive notification that the test was successfully performed and that teriflunomide concentration is < 0.02 mg/L (actual concentration will not be displayed). A second test will be performed approximately 15 days after the first test to confirm the result.
- If plasma teriflunomide concentration is more than 0.02 mg/L, site will receive notification that teriflunomide plasma level is ≥ 0.02 mg/L and the actual concentration will be displayed on the report. In such a case, the accelerated elimination procedure

5 December 2018, page 114/376

may be repeated at the discretion of the investigator and the subject will be instructed to continue contraception until at least 6 weeks after the first of two consecutive tests that show teriflunomide plasma concentration level below 0.02 mg/L.

For subjects continuing into the extension study AC-058B303 the applicable procedures for teriflunomide tests/retests and for continuation of contraception will be described in the AC-058B303 study protocol (separate protocol).

The duration of contraception after EOT should follow the following rules:

- For subjects continuing in the extension study AC-058B303 (separate protocol): the duration of contraception will be described in the AC-058B303 study protocol.
- For subjects not continuing in the extension study AC-058B303 (both males and females): the duration of contraception should always be until at least 6 weeks after the first of two consecutive tests that show teriflunomide plasma concentration level below 0.02 mg/L. Subjects who leave the study before achieving this should be instructed to follow this requirement outside the study.

5.2 **Previous and concomitant therapy**

5.2.1 Definitions

A previous therapy is any treatment for which the end date is prior to the start of study (i.e., signing of informed consent).

All therapy that is study concomitant (i.e., ongoing or initiated after signing of informed consent, and initiated before EOS visit) must be captured in the eCRF.

A therapy that is concomitant to study-treatment is any treatment that is either ongoing at the start of study treatment or is initiated during the study treatment period, or up to 30 days after the end of study treatment.

5.2.2 Reporting of previous/concomitant therapy in the eCRF

The use of all study-concomitant therapy (including contraceptives or traditional and alternative medicines, i.e., plant-, animal-, or mineral-based medicines) will be recorded in the eCRF. The generic name, start/end dates of administration (as well as whether it was ongoing at start of treatment and/or EOS), route, dose, and indication will be recorded in the eCRF.

Any previous administration of disease-modifying treatment for MS (IFN beta 1a [Rebif[®] - Avonex[®], Plegridy[®]], IFN beta 1b [Betaseron[®]], glatiramer acetate [Copaxone[®], Glatopa[®]], fingolimod [Gilenya[®]], dimethyl fumarate/BG-12 [Tecfidera[®]], natalizumab [Tysabri[®]], alemtuzumab [Lemtrada[®]]) at any time prior to screening will be recorded in

the previous MS treatment form of the eCRF. The start date, end date, dose, route, frequency, and reason for discontinuation will be recorded in the eCRF.

The therapies used for the treatment of relapses experienced by the subject in the past 24 months will be recorded in the previous MS treatment form of the eCRF (e.g., corticosteroids, ACTH). For each therapy, the start date, end date, reason for discontinuation, dose, route, and frequency of administration will be recorded in the eCRF.

Any previous relevant therapy as per principal investigator / treating neurologist judgment (e.g., therapies listed in exclusion criteria, therapies for relevant medical history) will be recorded in the previous therapy form of the eCRF.

5.2.3 Recommended concomitant therapy

Treatment of relapses:

- If a relapse requires treatment with corticosteroids, methylprednisolone 1 g i.v. daily for 3 to 5 days is recommended. Treatment with other corticosteroids, another dose, other routes of administration, or ACTH is not recommended unless deemed absolutely necessary and must be documented in the patient charts by the investigator. Oral taper with corticosteroids should not be administered in any case.
- Treatment of relapses with plasma exchange (i.e., plasmapheresis, cytapheresis) is prohibited.

5.2.4 Allowed concomitant therapy

- Dalfampridine (synonymous with fampridine) on a stable dose for at least 90 days prior to randomization and during double-blind treatment. Dalfampridine therapy must not be started or increased in dose during the study. Stopping or decreasing the dose of dalfampridine during the study should only take place if deemed absolutely necessary and must be documented in the patient charts by the investigator;
- Administration of i.v. atropine in the event of symptomatic bradycardia;
- Short-acting ß2-agonists for respiratory symptoms and/or reduced pulmonary function during study drug treatment;
- QT-prolonging drugs with known risk of Torsades de Pointes should be used with caution since ponesimod may potentially enhance their effect on QT interval [guidance is provided in Appendix 3];
- Vaccination with non-live vaccines. Subjects receiving non-live vaccination while on study treatment will have 5 mL of blood drawn prior to and ≥ 3 weeks after vaccination in order to assess changes in vaccine-specific antibody titers from pre- to post-vaccination. Samples will be analyzed at the end of the study [see Section 3.1.6.4].

• The following medications should be administered with caution due to potential interaction with teriflunomide:

- Teriflunomide is an inhibitor of cytochrome P450 (CYP)2C8 *in vivo*: CYP2C8 substrates such as repaglinide, paclitaxel, pioglitazone, or rosiglitazone should be carefully monitored when co-administered with study drug treatment as they may have higher exposure;
- Teriflunomide may be a weak inducer of CYP1A2 *in vivo*: medicinal products metabolized by CYP1A2 such as duloxetin, alosetron, theophylline and tizanidine should be used with caution during study drug treatment, as reduction of the efficacy of these products may be observed;
- A 25% decrease in peak INR was observed when teriflunomide was co-administered with warfarin as compared with warfarin alone. Therefore, when warfarin is co-administered with study drug treatment, close INR FU and monitoring is recommended;
- Teriflunomide is an inhibitor of organic anion transporter (OAT)3 *in vivo*: when study drug treatment is co-administered with substrates of OAT3, such as cefaclor, benzylpenicillin, ciprofloxacin, indometacin, ketoprofen, furosemide, cimetidine, zidovudine, caution is recommended;
- Co-administration of substrates of breast cancer resistant protein (e.g., topotecan, sulfasalazine, daunorubicin, doxorubicin) and the OAT polypeptide family (e.g., nateglinide, repaglinide, rifampicin) and especially HMG-CoA reductase inhibitors (e.g., rosuvastatin, simvastatin, atorvastatin, pravastatin) with the study drug treatment should be undertaken with caution. Subjects should be closely monitored for signs and symptoms of excessive exposure to these medicinal products, and reduction of the dose of these medicinal products should be considered;
- Rifampicin and other known potent CYP and transporter inducers such as carbamazepine, phenobarbital, phenytoin and St John's Wort may result in a decrease in teriflunomide exposure. Co-administration of these drugs with study drug treatment should be used with caution.
- Other treatments considered necessary for the subject's wellbeing and not categorized as prohibited concomitant medications.

5.2.5 Forbidden study-treatment-concomitant therapy

• Systemic corticosteroids and ACTH, except for the treatment of MS relapses [see Section 5.2.3] and for short-term treatment (up to 2 weeks per treatment cycle with at least 8 weeks' interval between treatment cycles and no more than 8 weeks during the

5 December 2018, page 117/376

whole study duration) with low dose of corticosteroid (up to 10 mg of prednisone equivalent daily) or inhaled corticosteroids for pulmonary conditions;

- Disease-modifying drugs for MS other than prescribed as per protocol;
- Immunosuppressive treatment (e.g., cladribine, mitoxantrone or other systemic immunosuppressive treatments such as azathioprine, cyclophosphamide, cyclosporine or methotrexate);
- i.v. immunoglobulin;
- Plasmapheresis, cytapheresis, or total lymphoid irradiation;
- Vaccination with live vaccines;
- β-blockers, diltiazem, verapamil, digoxin, or any other anti-arrhythmic or HR-lowering systemic therapy [non-exhaustive list of drugs provided in Appendix 4];
- Cholestyramine or activated charcoal unless needed for an accelerated elimination procedure;
- Any other investigational drug;
- Any investigational therapeutic procedure for MS (e.g., stent placement or angioplasty for chronic cerebrospinal venous insufficiency, stem-cell transplantation).

In the event that a subject takes any of these forbidden medications, the investigator must contact the sponsor to discuss further FU actions including stopping/interrupting study treatment as appropriate.

6 STUDY ENDPOINTS

For each of the study endpoints, baseline is defined as the last value recorded prior to randomization (the actual visit used as baseline might be different across endpoints).

6.1 Efficacy endpoints

6.1.1 **Primary efficacy endpoint(s)**

The primary endpoint is ARR. This endpoint is based on the number of confirmed relapses per subject-year.

Definition of relapse

• A relapse is defined as new, worsening or recurrent neurological symptoms that occur at least 30 days after the onset of a preceding relapse, and that last at least 24 h, in the absence of fever or infection.

The new, worsening or recurrent neurological symptoms are to be evaluated by the treating neurologist and, if all the elements of the above definition have been verified, and in the absence of another, better explanation of the subject's symptoms, the event is considered

as a relapse [see Section 7.2.2]. The onset date of the relapse corresponds to the onset date of the symptoms.

- A relapse will be confirmed by the treating neurologist only when the subjects' symptoms are accompanied by an increase in EDSS/FS scores, which is consistent with the subject's symptoms, from a previous clinically stable EDSS/FS assessment (i.e., performed at least 30 days after the onset of any previous relapse), obtained by the efficacy assessor and consistent with the following:
 - An increase of at least half a step (0.5 points; unless EDSS = 0, then an increase of at least 1.0 points is required) or
 - An increase of at least 1.0 point in at least two FS scores, or
 - An increase of at least 2.0 points in at least one FS score (excluding bladder/bowel and cerebral).

6.1.2 Secondary efficacy endpoints

There are four secondary efficacy endpoints, which will be analyzed as per the statistical testing strategy outlined in Section 11.3.1:

- Change from baseline to Week 108 in fatigue-related symptoms as measured by the symptoms domain of the FSIQ-RMS
- Cumulative number of combined unique active lesions (CUAL) from baseline to Week 108

Definition: CUAL are new Gd+ T1 lesions plus new or enlarging T2 lesions (without double-counting of lesions).

• Time to 12-week CDA from baseline to EOS

Definition: A 12-week CDA is an increase of at least 1.5 in EDSS for subjects with a baseline EDSS score of 0.0 or an increase of at least 1.0 in EDSS for subjects with a baseline EDSS score of 1.0 to 5.0, or an increase of at least 0.5 in EDSS for subjects with a baseline EDSS score \geq 5.5 which is to be confirmed after 12 weeks.

Baseline EDSS is defined as the last EDSS score recorded prior to randomization. The initial EDSS increase, meeting the above criteria, is defined as the onset of disability accumulation.

All EDSS measurements (with or without relapse, at a scheduled or unscheduled visit) will be used to determine the onset of disability accumulation. However, EDSS scores used for confirmation of disability accumulation must be obtained at a scheduled visit (i.e., unscheduled visits cannot be used as confirmatory visits) outside any ongoing relapse. In this context, relapse duration is defined as period between start and end dates if available Ponesimod / ACT-128800 Relapsing multiple sclerosis Protocol AC-058B301, OPTIMUM Version 7 5 December 2018, page 119/376

Confidential

and limited to 90 days from onset if end date is not available or duration is longer than 90 days.

In order to confirm that the EDSS increase is persistent, all EDSS measurements between the onset and the 12-week EDSS confirmation (minus 7-day visit time-window) need to show an increase in EDSS, meeting the criteria for accumulation of disability as defined above.

• Time to 24-week CDA from baseline to EOS

Definition: A 24-week CDA is an increase of at least 1.5 in EDSS for subjects with a baseline EDSS score of 0.0 or an increase of at least 1.0 in EDSS for subjects with a baseline EDSS score of 1.0 to 5.0, or an increase of at least 0.5 in EDSS for subjects with a baseline EDSS score \geq 5.5 which is to be confirmed after 24 weeks.

Baseline EDSS is defined as the last EDSS score recorded prior to randomization. The initial EDSS increase, meeting the above criteria, is defined as the onset of disability accumulation.

All EDSS measurements (with or without relapse, at a scheduled or unscheduled visit) will be used to determine the onset of disability accumulation. However, EDSS scores used for confirmation of disability accumulation must be obtained at a scheduled visit (i.e., unscheduled visits cannot be used as confirmatory visits) outside any ongoing relapse. In this context, relapse duration is defined as period between start and end dates if available and limited to 90 days from onset if end date is not available or duration is longer than 90 days.

In order to confirm that the EDSS increase is persistent, all EDSS measurements between the onset and the 24-week EDSS confirmation (minus 7-day visit time-window) need to show an increase in EDSS, meeting the criteria for accumulation of disability as defined above.

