If a secondary endpoint listed as part of the fallback procedure above is successful, the preserved alpha is passed along to the next secondary endpoint in the sequence and the summed alpha is used for testing that endpoint. Thus, as sequential tests are successful, the alpha accumulates for the endpoints later in the sequence; these endpoints are then potentially tested with a progressively larger alpha, but always with at least 1/3 of the alpha.

In a last step, the secondary endpoint

• Time to 24-week CDA from baseline to EOS [24-week CDA]

is tested in a subsequent stage following Time to 12-week CDA with the remaining alpha.

A graphical description of this testing strategy for the primary and secondary endpoints following the approach from Bretz, et al. [Bretz 2009] is provided in Figure 8 Overall testing strategy.

Based on the latest published information from recent MS trials, the disability accumulation rate is expected to be lower than assumed in earlier protocol versions [Cohen 2018, Comi 2018]. This results in a lower than anticipated probability of the study providing a robust evaluation of the effect of ponesimod on disability accumulation and, consequently, would have limited the ability to assess the other secondary endpoints with the previously planned hierarchical multiple testing strategy. The sponsor considers that the introduced fallback type multiple testing strategy optimizes the ability of the trial to obtain conclusive results on key disease parameters.

Analyses for secondary endpoints will be conducted at an overall two-sided 5% alpha level, with multiplicity adjustment as per the above testing strategy. 95% confidence intervals will be presented. The statistical analyses sections and sample size calculations for the secondary endpoints have been updated accordingly.

Additional minor changes and clarifications were made to the protocol as follows:

- Cladribine was added to the list of orally administered disease-modifying therapies.
- It was clarified that oral taper of corticosteroids should not be administered in order to harmonize the treatment of relapses in the study and to minimize the risk of combined immunosuppression.
- It was clarified that No evidence of disease activity (NEDA) status will be considered up to EOS.
- It was corrected that health care utilization will be not be displayed by visit.

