12-lead ECG*	* (9)	Х	Х	Х	Х	Х	Х		Х	X(9)	Х	
Pulse rate*								Х	X(20)			
Ophthalmological examination / OCT*					×				х			
Pulmonary fur	nction tests** (11)				Х	Х	Х		Х			
Hematology/C	Chemistry**(fasted)	Х	Х	Х	Х	Х	Х		Х			
Urinalysis	•		Х		Х	Х			Х			
Viral serology	,	1							Х			
Pregnancy tes	t*/** (12)	Х	Х	Х	Х	Х	X (12)		Х			
Serum sample	vaccination* (13)								Х			

Ponesimod / ACT-128800 Relapsing multiple sclerosis Protocol AC-058B301, OPTIMUM Version 7

Confidential

EudraCT 2012-000540-10 Doc No D-18.388

5 December 2018, page 49/376

PK sampling for ponesimod*				Х				X (14)		
Teriflunomide plasma concentration								X (23)		
Accelerated elimination procedure				Х	X (15)					
Accelerated elimination procedure					x	X (24)				
compliance review						,				
Study drug dispensing/accountability (16)	Х	Х	Х	Х			Х	Х	Х	Х
AEs/SAEs* (17)	Х	Х	Х	Х	Х	Х	Х	Х	Х	х

*Data collected in the eCRF

**Electronically transferred to sponsor.

Day 1 (date of randomization visit) is to be used as the reference date for the purpose of calculating the subsequent visit dates (and time windows).

- (1) At every study visit, subjects are reminded to contact their principal investigator / treating neurologist at the clinical site immediately in the event of the appearance of any new or worsening neurological symptoms. In addition, the site will contact the subject in between the 12-weekly visits (e.g., Visit 6–Week 12, Visit 7–Week 24,...) in order to proactively inquire about any new or worsened neurological symptoms. These telephone calls will be conducted either at Weeks 18, 30, 42, 54, 66, 78, 90, and 102 (+/- 7 days), or 6 weeks after the last 12-weekly visit (+/- 7 days). Whenever, between visits, a subject experiences any new or worsening neurological symptoms, he/she must contact the principal investigator / treating neurologist, study nurse or clinical coordinator as soon as possible in order to complete a relapse assessment questionnaire [see Appendix 17].
- (2) The symptoms scale (with a 24-h recall) will be completed for 7 consecutive days (the day of the visit and the 6 days after the visit).
- (3) Health care resource utilization data, number of intensive care unit admission for MS relapses and emergency medical services facility visits for MS.
- (4) Only for subjects-participating in the patient preference sub-study. The Multiple Sclerosis Patient Preference Questionnaire will be completed at home during follow-up period (before Visit 15 [FU1]).

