7.2 Efficacy assessments

7.2.1 Neurological evaluation

EDSS and FS scores [Kurtzke 1983] are based on a standard neurological examination for assessing neurologic disability and impairment in MS. The seven FS scores are ordinal clinical rating scales ranging from 0 to 5 or 6, assessing visual, brain stem, pyramidal, cerebellar, sensory, bowel and bladder, and cerebral functions while ambulation is an ordinal scale ranging from 0 to 12 assessing walking distance and assistance. The ratings of the individual FS scores are then used, in conjunction with ambulation score, to obtain the EDSS score. EDSS is an ordinal clinical rating scale ranging from 0 (normal neurological examination) to 10 (death due to MS) in half-point increments.

EDSS and FS assessments will be performed at Visits 1 (Screening), 2 (Baseline), 6 to 13 (Week 12 and every 12 weeks thereafter), 14 (EOT), 16 (FU2), and at any unscheduled visit in the event of relapses (R1, R2, etc.) or other unscheduled visits (U1, U2, etc.). If applicable, EDSS and FS will also be assessed at the corresponding visits in the PTOP (Visits 6A to 14A).

EDSS and FS assessments will only be performed by the efficacy assessor who should preferably maintain this role for a given subject throughout the study [see Section 3.3.3]. The efficacy assessor must not consult prior EDSS/FS scores when performing the current EDSS/FS assessment. In no case will the treating neurologist alter the EDSS/FS score obtained by the efficacy assessor. The examination will be based on the modified neurological examination "Neurostatus" [Appendix 2] using the corresponding scoring documents. The EDSS/FS score will be recorded in the eCRF. NB: Fatigue, which is an optional part of the Neurostatus assessment will not contribute to the Cerebral FS score.

Ponesimod / ACT-128800 Relapsing multiple sclerosis Protocol AC-058B301, OPTIMUM Version 7 5 December 2018, page 125/376

Confidential

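### CDA confirmation deducts one 7-day visit window although both EDSS visits have one, so some on-schedule visit pairs are too close to confirm and a small share of events can be lost

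*Protocol*

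**What the plan says.** Section 6.1.2 defines onset of disability accumulation as the first qualifying EDSS rise: "The initial EDSS increase, meeting the above criteria, is defined as the onset of disability accumulation". Any EDSS, scheduled or not, can mark onset. Confirmation is stricter: "EDSS scores used for confirmation of disability accumulation must be obtained at a scheduled visit", outside an ongoing relapse, and "unscheduled visits cannot be used as confirmatory visits". Persistence must be shown at "all EDSS measurements between the onset and the 12-week EDSS confirmation (minus 7-day visit time-window") for the 12-week endpoint and at "all EDSS measurements between the onset and the 24-week EDSS confirmation (minus 7-day visit time-window") for the 24-week endpoint.

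Section 7.2.1 places EDSS assessments after baseline at Visits "6 to 13 (Week 12 and every 12 weeks thereafter), 14 (EOT), 16 (FU2"), with matching visits in the post-treatment observation period (PTOP). Tables 1 to 3 give every 12-weekly visit, including EOT and the PTOP visits, a window of 7 days either side. The notes to those tables state that Day 1 "is to be used as the reference date for the purpose of calculating the subsequent visit dates (and time windows").

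Under Section 3.1.4, completers who enter the extension finish at FU1 or at an abbreviated FU2. Table 2 schedules no EDSS at FU1, and its note 22 lists the content of the abbreviated FU2 without an EDSS.

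**The concern.** The allowance is described as a visit window, but it covers the deviation of one visit only. The interval between onset and confirmation depends on two visits, and because both windows are counted from Day 1 their deviations can add. A late onset visit followed by an early next visit gives a pair in which both visits comply with the schedule, both may show the qualifying increase, and the second still does not confirm.

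No unscheduled visit can fill the gap. The subject must still qualify at the next scheduled EDSS about 12 weeks later, so for that subject 12-week CDA in effect asks for about 24 weeks of persistence. If no later scheduled EDSS exists, the event cannot be confirmed at all. Two of the four secondary endpoints, both in the alpha-controlled testing sequence, use this rule, and 12-week CDA also enters the NEDA definition.

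**Working it through.** The available protocol text states no figure for this point, so there is nothing to reproduce. The check is day arithmetic on the protocol's own windows.

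**Inputs**
- Minimum interval, literal reading of Section 6.1.2: 12 × 7 − 7 = 77 days; 24 × 7 − 7 = 161 days.
- Visit deviation, Tables 1 to 3: −7 to +7 days from a nominal date counted from Day 1, for each visit separately.

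**Range of compliant intervals.** With onset visit at deviation a and confirming visit at deviation b, the interval is 84 + b − a, or 168 + b − a.
- 12-week: 84 − 14 = 70 to 84 + 14 = 98 days. Intervals of 70 to 76 days fail.
- 24-week: 168 − 14 = 154 to 168 + 14 = 182 days. Intervals of 154 to 160 days fail.

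**Share of visit pairs that fail.** Both endpoints fail when a − b is 8 or more, so the shares are the same. Visit timing is an assumption, because the protocol gives no distribution.
- Uniform over the 15 days: a − b = 8, 9, …, 14 occurs in 7 + 6 + 5 + 4 + 3 + 2 + 1 = 28 of 15 × 15 = 225 pairs, or 12.4%.
- Triangular, peaked on the nominal day: 210/4096 = 5.1%.
- Bell-shaped: 6.1% (SD 4 days), 3.1% (SD 3), 0.4% (SD 2).
- All visits within 3 days of nominal: a − b is at most 6, so 0%.

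**Last-interval case, 12-week CDA.** The latest Week 96 visit is day 672 + 7 = 679 from the Day 1 reference. The earliest Week 108 visit is day 756 − 7 = 749. The interval is 70 days, below 77. An extension entrant has no later EDSS, so the event is lost. A subject with a full FU2, at the earliest 30 days after a last dose on day 748, has an EDSS on day 778; 778 − 679 = 99 days, which can confirm.

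**Last-interval case, 24-week CDA.** The latest Week 84 visit is day 588 + 7 = 595; 749 − 595 = 154 days, below 161. A full FU2 would give 778 − 595 = 183 days.

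The loss also applies to PTOP subjects whose last visit is Week 108 of the PTOP.

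**Share of 12-week events lost outright.** Suppose onset is spread evenly over the eight visits from Week 12 to Week 96. Last-interval loss alone is then at most 12.4%/8 = 1.6% (uniform) or 5.1%/8 = 0.6% (triangular), before multiplying by the share without a later EDSS. A simulation with 80 to 100% of subjects lacking a later EDSS, and 0 to 30% of increases gone by the following visit, gave:

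| Visit timing | 12-week events lost |
|---|---|
| Uniform | about 1.3% to 4.9% |
| Bell-shaped, SD 3 days | about 0.3% to 1.2% |
| Bell-shaped, SD 2 days | at most 0.15% |

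**After correction.** With a minimum of 70 or 154 days, 0 of 225 pairs fail.

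**The case against.** The 77- and 161-day minima are inferred from a parenthesis; Section 6.1.2 states no minimum in days. Sections 11.2.2.3 and 11.2.2.4, which define the two variables, were not in the text available for this review, and a SAP would be the usual place for an exact day rule. This stands as a limit: the point concerns the literal wording of Section 6.1.2.

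A strict minimum can also be deliberate, since it protects against counting transient worsening. The rationale for Amendment 6 says the confirmation rule was clarified partly to limit the influence of short-term relapse-related disability. That is a fair reason to keep the definition. It does not explain a schedule that allows visits too close to satisfy it, and the same sentence of the rationale also aims to make the fullest use of the data.

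A reader might infer four stronger things that the documents do not support:
- That event times are delayed. Onset stays at the initial increase, so only confirmation moves.
- That 12.4% of events are lost. That figure is a share of visit-day pairs under uniform timing. Most earlier events can still be confirmed at a later visit, and the calculation does not describe onsets at unscheduled or relapse visits.
- That the comparison is biased. Nothing in the text makes visit timing differ between arms.
- That fewer events are expected than now planned. The rationale says "the disability accumulation rate is expected to be lower than assumed in earlier protocol versions", and it adds that the secondary-endpoint sample size calculations were updated.

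**Conclusion.** The mismatch holds on the literal text: one 7-day allowance does not cover two 7-day windows (70 is below 77, and 154 is below 161). Its usual consequence is a confirmation about 12 weeks later with an unchanged onset date.

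Outright loss needs a too-close pair together with one of two conditions. Either the increase no longer qualifies by the next usable visit, or there is no later scheduled EDSS. The second applies to Week 96 onset (12-week CDA) or Week 84 onset (24-week CDA) in extension entrants, or in PTOP subjects whose last visit is Week 108.

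The loss is about 0 to 5% of 12-week events, depending on assumed visit timing, onset distribution, extension entry and persistence. The lower end is the more likely if sites keep close to nominal dates. The result is a small loss of events and power. It is worth correcting because the correction is cheap.

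**What to change.** Add one scheduling rule to Tables 1 to 3 and Section 7.2.1 for the visits still to come. Within the existing windows, each 12-weekly EDSS visit (including Week 108/EOT and PTOP visits) is booked at least 77 days after the previous one and at least 161 days after the one before that. For in-window visits this is always feasible: the rule needs a deviation of at least a − 7 for each of the two earlier visits, and since a is at most +7, booking on the nominal day always satisfies both limits. The CDA definition stays as it is.

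The cost is one sentence, a scheduling check at sites and a narrower booking range for some visits. No visit or assessment is added.

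The rule cannot repair visits already held. For those, the sponsor could, before unblinding, either define the confirming visit by its nominal scheduled visit or state a minimum interval that covers both windows (70 and 154 days). The choice should be the same for both CDA endpoints. The price is a slightly shorter required persistence for some events.
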